4.4 Sample size

According to the literature and previous data in this study, 75% of the subjects will have the event of interest (disappearance of symptoms) by day 21. Thus, including 390 subjects, we will identify 290 events of interest. With this sample size we will have a power of 80% and an Alpha of 0.05 to detect a Hazard ratio of 1.4 of ivermectin vs. placebo in time to symptom resolution. Taking into account a 2 % follow-up loss and 76 subjects who will be excluded from the primary analysis¹, we will include a total of 476 subjects in the study.

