4.5 Data analysis

An interim analysis will be conducted without breaking the blind when 200 research participants have been randomized. The study will be discontinued if this analysis detects a significant treatment effect on the main objective, if it is detected that a significantly larger group of subjects withdraw from the intervention arm due to adverse events, or if no difference is detected between the two groups. Recruitment will continue while this analysis is performed.

The information will be analyzed with Stata version 14 (SE; Stata corporation, College Station, Texas). For this purpose, subjects will be grouped into 2 groups that comprise

- Group 1:** Subjects who received ivermectin
- Group 2:** Subjects who received placebo.

The baseline characteristics of the subjects will be described by descriptive analysis.

The main analysis will be by intent-to-treat. The time until the disappearance of symptoms will be determined when all research subjects reach day 21. Clinical deterioration or death before the 21st will be right censored- on the 21st. Deaths will be included unless there is strong evidence that the cause of death was not associated with COVID-19. The time until the disappearance of symptoms will be presented in a Kaplan-Meier curve and will be compared with the log-rank test. Hazard Ratios will be calculated with their 95% confidence interval through a Cox proportional-hazards model.

¹ 76 subjects included in the study had errors in the enlistment of the investigation product consecutively for three weeks, and will be excluded from the primary analysis.

Secondary outcomes and adverse events in each of the groups will be expressed by absolute and relative frequencies with their corresponding 95% confidence interval. For the univariate analysis in the quantitative variables, statistical parameters of central tendency and dispersion (means and standard deviations) will be described if the variable has a normal distribution. In case of not having a normal distribution, medians and interquartile ranges will be described. The qualitative variables will be measured and analyzed through proportions with their corresponding 95% confidence interval.

To determine the efficacy of the intervention in secondary outcomes, a bivariate analysis will be performed, evaluating the association of treatment, demographic and clinical variables with the different outcomes.

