4.1. Primary outcome

-Time until the resolution of the symptoms in the two study groups. Number of days from randomization visit to the first symptom-free day (score of 0 on the 8-point scale). Variable measured during the 21 days of follow-up.

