6.1. Primary outcome

The main analysis will be the survival analysis for the primary outcome variable (time to disappearance of symptoms associated with COVID-19), using the log-rank test to compare ivermectin versus placebo as a control group. Symptom resolution will be assessed using the 8-point ordinal scale, which has the following categories: (0) -Patient without symptoms, (1) -Non-hospitalized patient, with the ability to do daily activities, (2) -Non-hospitalized patient, unable to do daily activities, or using oxygen at home (3) -Hospitalized, without need for supplemental oxygen, (4) -Hospitalized, with need for supplemental oxygen, (5) -Hospitalized, with need for high-flow nasal oxygen or non-invasive mechanical ventilation, (6) -Hospitalized, in need of mechanical ventilation or ECMO, (7) -Death.

The outcome variable will be the time to recovery, defined as the first day, during the 21 days of follow-up, in which the patient reports a score of (0) on the 8-point scale.

Patients who do not report recovery from symptoms and those who die during study follow-up will be considered as censor data on day 21 or until death. Kaplan-Meier estimator will be used to report the recovery percentage throughout the follow-up and at day 21. Relevant treatment efficacy parameter is the recovery rate ratio (RR) with its respective 95% confidence interval (CI), which will be estimated by Cox proportional-hazard model. Given that the primary outcome may take two values; equal to 1 when the patient reports recovery of symptoms and 0 when not, a $RR > 1$ will indicate a favorable result for ivermectin compared to placebo.

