6.5. Handling missing data

Primary outcome:

The primary outcome is expected to be available in all patients. In the event that the patient dies during follow-up, a censoring for the study will be considered until the time of last observation. If the patient is lost to follow-up, last report on the 8-point scale during follow-up will be considered as the outcome.

Covariates: If there are missing data in the variables needed to analyze for effect modification, and this may have an effect the primary outcomes of the study, then simple imputation will be performed using the median of the treatment group to which the observation belongs based on the information reported in the sample with complete data.

Secondary outcomes. Data will not be imputed. The percentage of missing data will be reported.

Summary of Changes in the Statistical Analysis Plan

1. Introduction:

The original primary outcome (time until worsening in 2 or more points in the 7-point ordinal scale) was replaced by the final primary outcome (time to resolution of symptoms)

2.2 Sample size calculation:

The original sample size was calculated to 400, in order to detect a hazard ratio in time to deterioration of 0.5 of ivermectin vs. placebo. The sample size remained 400 patients, after the primary endpoint was modified. However, the sample size increased to 476 due to 76 patients who were excluded from primary analysis (76 subjects who had errors in the label of the investigation product consecutively for three weeks)

4.1 primary outcome

The primary outcome was changed to Time until resolution of symptoms in the two study groups

4.2 secondary outcomes

The primary outcome became a secondary outcome. The ordinal scale changed from 7 to 8 points to include the score of 0.

The proportion of subjects who develop fever was added as an indirect marker of the antiviral capacity of the drug

6. Analysis Plan

The STATA version was updated to 16.0

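### Protocol and SAP give conflicting rules for death, deterioration and loss in the primary time-to-recovery analysis, and one rule should be fixed in advance

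*Supplement*

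**What the plan says.** All references are to the latest protocol (476 participants) and the SAP of 20 September 2020. The event is the first score of 0 on the 8-point scale within 21 days of randomisation (SAP 4.1, 6.1).

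- **Death, timing.** Protocol 4.5: "Clinical deterioration or death before the 21st will be right censored- on the 21st". SAP 6.1: "those who die during study follow-up will be considered as censor data on day 21 or until death". SAP 6.5: "In the event that the patient dies during follow-up, a censoring for the study will be considered until the time of last observation".
- **Death, inclusion.** Protocol 4.5: "Deaths will be included unless there is strong evidence that the cause of death was not associated with COVID-19". The same section calls the main analysis intent-to-treat, and SAP 5.1 defines that population as everyone randomised, analysed as assigned.
- **Deterioration.** Protocol 4.5 puts it in the same censoring sentence as death. That sentence also stood in the protocol when deterioration was the primary endpoint. SAP 6.1 has no deterioration rule and takes the first score of 0, whatever came before.
- **Loss.** SAP 6.5: "If the patient is lost to follow-up, last report on the 8-point scale during follow-up will be considered as the outcome". It gives no time at which the patient leaves the risk set. The same section expects the outcome to be available for everyone, while protocol 4.4 and SAP 2.2 allow for 2% loss.
- **Sensitivity.** The only one planned for the primary outcome is per protocol (SAP 6.3), and SAP 5.1 ties that population to complete data.

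**The concern.** The same patient can be a recovery, censored early or censored on day 21, depending on which section the analyst follows. Each choice can be defended from the text after the data have been seen.

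The rules also differ in meaning. A patient who has died cannot become symptom-free. Censoring at death or last observation gives that patient the survivors' later chance of recovery, which weakens the signal from an excess of deaths in one arm. Keeping the patient at risk and unrecovered to day 21 does not. Censoring a patient who worsened and then recovered discards a real event. Taking the last score as the outcome for a lost patient, if it means unrecovered to day 21, turns a difference in dropout into an apparent treatment difference. The per-protocol run cannot test this, because it requires complete data.

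**Working it through.** **1. The plan's own figure.** Protocol 4.4 assumes 75% recovery by day 21, 390 analysed and 290 events, for 80% power at alpha 0.05. The stated aim is "to detect a Hazard ratio of 1.4 of ivermectin vs. placebo in time to symptom resolution". Sidedness is not stated; two-sided is assumed (one-sided gives 219 to 223 events and does not fit).

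- Freedman: (1.960 + 0.8416)² × (2.4/0.4)² = 7.849 × 36 = 282.6, so 283 events.
- Schoenfeld: 4 × 7.849 / (ln 1.4)² = 31.40 / 0.1132 = 277.3, so 278 events.
- Power at 290 events: 0.810 (Freedman) or 0.817 (Schoenfeld).
- 390 × 0.75 = 292.5 events; 390/0.98 = 398; 398 + 76 = 474, against 476 stated.

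The sample size reproduces and is not affected. The 95% CI factor at 290 events is exp(1.96 × 2/√290) = 1.26, so an HR of 1.40 has an interval of 1.11 to 1.76.

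**2. The same patient under each rule** (illustrative days, no earlier score of 0).

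| Patient | Protocol 4.5 | SAP 6.1 | SAP 6.5 |
|---|---|---|---|
| Dies day 14, last contact day 11 | At risk to day 21, unless the cause is judged unrelated | Censored day 14 (day 21 also readable) | Censored day 11 |
| Worsens 2 points on day 5, score 0 on day 15 | Censored day 21 as written | Recovery on day 15 | No rule |
| Lost after day 4 with score 1 | No rule | Not addressed; non-recovery is censored on day 21 | Score 1 is the outcome, time not stated |

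A score of 0 is already the event, so anyone lost without one can only enter as not recovered.

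**3. Size.** Simulation with 1,000,000 per arm and exponential recovery. A placebo hazard of 0.0561 per day gives 1 − exp(−0.0561 × 21) = 69.2% recovered on placebo and 1 − exp(−1.4 × 0.0561 × 21) = 80.8% on ivermectin, mean 75%.

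Assumptions: deaths uniform over days 5 to 21; losses uniform over days 1 to 21 and unrelated to prognosis; deterioration delays recovery by 7 days. Death scenarios carry 2% loss per arm; loss scenarios carry 1% deaths per arm. The documents give no rates by arm. Their guides are pooled: under 3% deterioration (Summary of Changes, Amendment 3) and 2% loss. The first also limits deaths, because entry scores reach at most 4 and a death is then a rise of at least 3 points.

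| Rule compared | Placebo/ivermectin | First rule | Second rule | Shift |
|---|---|---|---|---|
| Death: censored at death vs kept to day 21 | 1%/1% | 1.400 | 1.396 | −0.004 |
| | 3%/3% | 1.393 | 1.383 | −0.010 |
| | 3%/1% | 1.427 | 1.440 | +0.013 |
| | 1%/3% | 1.361 | 1.336 | −0.025 |
| | 3%/0% | 1.447 | 1.472 | +0.025 |
| | 0%/3% | 1.349 | 1.317 | −0.032 |
| Deterioration: later recovery counted vs censored day 21 | 3%/3% | 1.396 | 1.380 | −0.016 |
| | 3%/1% | 1.416 | 1.441 | +0.025 |
| | 1%/3% | 1.377 | 1.331 | −0.046 |
| Loss: censored at last contact vs carried to day 21 | 4%/0% | 1.393 | 1.423 | +0.030 |
| | 0%/4% | 1.397 | 1.364 | −0.033 |

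Equal 2% loss shifts the HR by at most 0.003. Monte Carlo error is up to about 0.005 (the run without deaths or losses gave 1.395).

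**4. Under no effect.** With equal rates in the arms, every rule gives 0.998 to 1.001. With 4% lost from ivermectin and none from placebo, carry-forward gives 0.980 if losses are spread over days 1 to 21 and 0.953 if all fall in the first 8 days. With 3% against 1% it gives 0.991 and 0.979. Censoring at last contact gives about 1.00.

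**5. Beyond those rates.** The regional fatality of 6.5% (protocol section 2), placed in one arm only, gives 1.501 vs 1.559 (placebo) or 1.283 vs 1.220 (ivermectin). Pooled, that is 6.5/2 = 3.25% deaths, above the observed rate for all deterioration. Loss of 5% on placebo and 15% on ivermectin gives 1.398 vs 1.311.

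**6. Events in dispute over deterioration.** At most 3% × 400 = 12 patients, and 12/290 = 4%. This ceiling needs every one of them to be symptom-free by day 21.

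**The case against.** A reader might infer that the plan treats all deaths as non-informative, carries lost patients forward as unrecovered, and so biases its primary hazard ratio. The documents do not support that much.

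- Protocol 4.5 already keeps deaths at risk to day 21, the rule recommended here. The defect is that the SAP says something else.
- Carrying losses to day 21 is an inference. SAP 6.1's general treatment of non-recovery makes it the likely reading of SAP 6.5, but censoring at last contact is not ruled out.
- Bias needs imbalance. The only stated loss rate is 2%, and the current placebo is matched in taste, smell, texture and appearance (protocol 4.3.4). Putting all loss in one arm, and early, is a severe assumption.
- Deaths are not hidden from the report. Death is category 7 in the ordinal regression at each visit, it counts as deterioration, and protocol 4.1.5.2 lists death within 21 days.
- The cause-of-death sentence stands beside the intent-to-treat statement and has no counterpart in the SAP, so removal of patients is permitted by the wording rather than established.
- The deterioration sentence could be meant only for patients who never recover. It does not say so.

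These points limit the size and tone of the criticism. They do not supply a single rule, and secondary analyses of death do not settle how the primary model handles it.

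**Conclusion.** The point holds as a contradiction in the definition of the primary analysis, not as a demonstrated bias. Death has three censoring times and a cause-dependent proviso at odds with the ITT definition. Recovery after deterioration is classified differently by protocol and SAP. Loss has no censoring time.

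With equal rates there is no bias under the null and only slight attenuation at an HR of 1.40. In the scenarios around the documents' rates, the choice of rule moves 1.40 by about 0.00 to 0.05, in a direction set by which arm has more deaths, deteriorations or losses. That is small beside a CI factor of 1.26, though it could matter for a result near the significance limit. Larger shifts need rates or imbalances that the documents do not suggest.

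The sizes rest on assumed rates by arm, event timing and exponential recovery, and the deterioration rule was varied separately from the death and loss rules. This should be fixed, at moderate priority.

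**What to change.** State one rule, in the same words, in protocol 4.5 and SAP 6.1 and 6.5:

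- Patients who die before recovering, whatever the cause, stay in the risk set as not recovered and are censored on day 21. This applies to all randomised patients; the separately stated exclusion of the 76 participants is a different matter.
- Deterioration is not a censoring event. A first score of 0 by day 21 is a recovery on that day.
- Loss to follow-up or withdrawal is censored at the last completed contact.
- One sensitivity analysis treats the lost as unrecovered to day 21.

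Delete the cause-of-death proviso, and delete the last-report rule for the primary outcome. Report deaths and losses by arm beside the hazard ratio.

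The cost is wording in three sections and one extra model. No new data are needed and the sample size is unchanged. It should be settled before the treatment codes are opened.

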6.2. Secondary outcomes

Secondary outcomes, hospitalization requirement, ICU or oxygen supplementation and deterioration in more than two points on the scale of clinical results will be analyzed through a Kaplan Meier estimate. Hazard ratio will be estimated by Cox proportional-hazard model. In addition, a logistic regression model in which each secondary outcome will be considered as the dependent variable (1: Event, 0: No event) and the intervention groups as the independent variable (1: ivermectin, 0: Placebo) will be used.

For each outcome, the odds ratio (OR) and its respective 95% CI will be reported. An OR > 1 is indicating favorable results in favor of placebo and an OR <1 in favor of ivermectin. In case of low frequency of individual outcomes, a combined variable will be created using need for hospitalization (general floor or ICU) and need for oxygen (by nasal cannula or mechanical ventilation) and will be analyzed using a logistic regression model reporting the OR with its 95% CI.

Evaluation of the effect of the treatment in each study visit using the 8-point ordinal scale will be estimated using the proportional OR with its respective 95% CI with an ordinal logistic regression. In this step, the 8-point ordinal scale will be inverted in its score, where 0 will correspond to death and 7 to a subject without symptoms. Thus, a proportional OR > 1 will indicate an effect in favor of ivermectin. The 95% confidence interval of the median difference in duration of fever and length of hospitalization or oxygen use will be estimated by bootstrap estimators.

6.3. Sensitivity Analysis and Modification of the Effect for the Primary outcome.

The analysis of the primary outcome will be repeated using the population under the per protocol approach and will be considered as sensitivity analysis. Additionally, if differences are found between the research product and the outcomes, it will be evaluated whether variables such as enrollment score on the 8-point scale, duration of symptoms before enrollment, comorbidities, age and sex, modify the effect of the intervention groups, using a multivariate Cox proportional hazards model. This will be done by including interaction terms to the model between the possible modifying variable and the intervention groups. A p value <0.10 will be considered as a possible modifying effect, and a p value <0.05 will be considered as a cut-off point to confirm a significant interaction and therefore, to estimate the effect of the treatment groups with their respective 95% CI.

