4.1.5.2. Secondary outcomes to be evaluated

- To determine the time to deterioration in two or more points of the 7-point ordinal scale in the two study groups.
- To determine the clinical state, using the 7-point ordinal scale, on days 2, 5, 8, 11, 15, and 21.
- The proportion of subjects requiring hospitalization, use of supplemental oxygen > 24 hours, admission to the ICU, or dying within 21 days in the two trial groups.
- The duration of supplemental oxygen in each arm of the study.
- The duration of hospitalization in each arm of the study.
- The duration of stay in the ICU in each arm of the study.
- The duration of fever (axillary temperature > 38C or subjective feeling of fever) in each arm of the study.
- Proportion of subjects who develop adverse events associated with the study drug.
- Proportion of subjects who required discontinuation of medication due to adverse events.

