| 6.3. Sensitivity Analysis and Modification of the Effect for the Primary Outcome | 9 |
| 6.4. Safety Analysis | ¡Error! Marcador no definido. |
| 6.5. Handling Missing Data..... | ¡Error! Marcador no definido. |

1. Introduction

The purpose of this study is to assess whether D11AX22 molecule (ivermectin) reduces the time to resolution of symptoms (primary outcome variable), as well as the proportion of hospitalization, use of supplementary oxygen and number of cases with fever or more than two points on the eight-point ordinal scale for COVID (secondary outcome variables), compared to placebo in subjects with mild COVID-19 disease. This document describes definitions and statistical methods to be used in order to fulfill EPIC trial aim and objectives.

2. Study Design

Double-blind, randomized, placebo-controlled clinical trial to evaluate the efficacy of the D11AX22 (ivermectin) molecule in adult subjects with mild SARS CoV2/COVID-19 disease at participating institutions in Valle del Cauca.

This study is a controlled clinical trial with two parallel group with an allocation ratio of 1:1. Ten clinical visits will be made at the following times: screening visit, randomization visit, day 2, day 3, day 4, day 5, day 8, day 11, day 15 and day 21.

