4.2. Secondary outcomes

-Proportion of cases with deterioration in two or more points of the 8-point ordinal scale in the two study groups. Proportion of subject who reported an increase in disease severity of 2 or more points on the 8-point ordinal scale relative to the randomization visit.

-Proportion of cases that required hospitalization, use of supplemental oxygen > 24 hours, and admission to the ICU.

-Duration of hospitalization, use of supplemental oxygen and duration of stay in ICU in each arm of the study.

-Clinical state, using the 8-point ordinal scale, on days 2, 5, 8, 11, 15, and 21.

-Proportion of cases who develop fever (axillary temperature > 38°C or subjective feeling of fever) in each arm of the study and duration of fever. Number of days from the randomization visit to an axillary temperature <38°C.

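### SAP section 1 and 6.2 count deterioration only above two points, where SAP 4.2 and the protocol say two or more; the protocol's death component is also missing from the SAP's event outcomes

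*Supplement*

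**What the plan says.** **Threshold for deterioration.** The latest protocol, 4.1.5.2, lists as a secondary outcome: "To determine the time to deterioration in two or more points of the 7-point ordinal scale in the two study groups". The latest SAP (September 2020), 4.2, agrees on the threshold: "Proportion of cases with deterioration in two or more points of the 8-point ordinal scale in the two study groups". It then gives the operational rule: "Proportion of subject who reported an increase in disease severity of 2 or more points on the 8-point ordinal scale relative to the randomization visit".

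Two other places in the same SAP differ. The introduction (section 1) names among the secondary variables the "number of cases with fever or more than two points on the eight-point ordinal scale for COVID (secondary outcome variables". Section 6.2, which sets out the Kaplan-Meier, Cox and logistic analyses, says "deterioration in more than two points on the scale of clinical results will be analyzed through a Kaplan Meier estimate".

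**Death.** Protocol 4.1.5.2 groups death with the other clinical events, ending its list with "admission to the ICU, or dying within 21 days in the two trial groups". The matching outcome in SAP 4.2 reads "Proportion of cases that required hospitalization, use of supplemental oxygen > 24 hours, and admission to the ICU" and stops there. The event outcomes in SAP 6.2 are hospitalisation, ICU, oxygen and deterioration, with no separate entry for death. If individual outcomes are rare, 6.2 adds that "a combined variable will be created using need for hospitalization (general floor or ICU) and need for oxygen (by nasal cannula or mechanical ventilation"); death is not a component. Death does remain category 7 of the ordinal scale (SAP 6.1) and the worst category of the by-visit ordinal regression (SAP 6.2).

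**The concern.** Section 6.2 is where a programmer would look for the analysis. If it is coded as written, a participant who worsens by exactly two points is a non-event, although 4.2 and the protocol call that participant an event. These are not marginal moves. They include an active outpatient who is admitted (1 to 3), an outpatient unable to do daily activities who is admitted and needs oxygen (2 to 4), and an inpatient on oxygen who needs mechanical ventilation (4 to 6). With few events expected, the reading chosen could settle the estimate, and the SAP does not say which section governs.

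The death gap is a separate matter. The logistic models in 6.2 code each outcome 1 for event and 0 for no event. Under that coding, a participant who dies with no recorded admission or oxygen gets the same 0 as a participant who stayed well. The Kaplan-Meier and Cox analyses of hospitalisation, oxygen and ICU have no rule for deaths. The SAP's censoring rules for deaths (6.1 and 6.5) are written for the primary outcome only.

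**Working it through.** **Inputs.**
- Scale: categories 1 to 6 of increasing severity and 7 for death (protocol 4.1.5.3). The SAP adds 0 for no symptoms (SAP 6.1).
- Highest eligible baseline: category 4, since mild illness allows inpatients on oxygen short of high-flow (protocol 4.1.5.3).
- Rate of deterioration by two or more points: under 3% of those included at the time of Amendment 3 (summary of changes).
- Number analysed: 476 − 76 = 400.

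**Check on the 3% figure.** Amendment 3 says that keeping deterioration as primary would need more than 2000 subjects. For a hazard ratio of 0.5, 80% power and alpha 0.05 (two-sided assumed), Schoenfeld's formula gives 4 × (1.96 + 0.842)² / (ln 0.5)² = 65.3, so 66 events. Then 66 / 0.03 = 2200. The plan's statement reproduces, so 3% can be used as its working ceiling.

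**Which moves depend on the threshold.**

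| Baseline | Events at ≥2 points | Events at >2 points | Lost under 6.2 |
|---|---|---|---|
| 1 | 3, 4, 5, 6, 7 | 4, 5, 6, 7 | 3 |
| 2 | 4, 5, 6, 7 | 5, 6, 7 | 4 |
| 3 | 5, 6, 7 | 6, 7 | 5 |
| 4 | 6, 7 | 7 | 6 |

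One destination is lost per baseline. If a baseline of 0 can occur, the move 0 to 2 is lost as well.

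**Whether deaths are affected by the threshold.** The rise to category 7 is 7 − baseline, that is 6, 5, 4 or 3 points from baselines 1 to 4. Each exceeds two, so death meets either threshold.

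**Size.** The ceiling at two or more points is 0.03 × 400 = 12 events (0.03 × 476 = 14 if all randomised are counted). The documents do not give the share that are exactly two-point moves, so a range is assumed:
- 25%: 12 × 0.75 = 9 events left
- 50%: 12 × 0.50 = 6 events left
- 75%: 12 × 0.25 = 3 events left

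**Death component, side by side.**

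| Place | Hospitalisation | Oxygen | ICU | Death |
|---|---|---|---|---|
| Protocol 4.1.5.2 | yes | yes | yes | yes |
| SAP 4.2 | yes | yes | yes | no |
| SAP 6.2 event outcomes | yes | yes | yes | only through deterioration |
| SAP 6.2 combined variable | yes | yes | yes | no |

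The combined variable misses only deaths with no recorded admission and no recorded oxygen need. The documents do not give that number.

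**The case against.** The best reply on the threshold is that this is loose wording and not a rival definition. SAP 4.2 is the section that defines outcomes, it states the rule against the randomisation score, and the protocol agrees. The SAP's summary of changes says the former primary outcome, at two or more points, became secondary, and it lists no change of threshold. The introduction's phrase is garbled and does not mention worsening. All of this stands, and two or more is the likelier intention. But the stricter wording appears twice, once in the section that specifies the analysis, so the text still has to be reconciled.

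On death, a reader might infer that mortality is never analysed. The documents do not support that. Death is the worst category of the by-visit ordinal regression, which includes day 21, and it is a rise of at least three points in the deterioration outcome. Protocol 4.5 also promises frequencies with confidence intervals for secondary outcomes, and these include death within 21 days. What stands is narrower: the SAP gives death no place of its own among the event outcomes and none in the combined variable.

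A reader might also infer that leaving out death causes worsening to be miscounted, or might add missed deaths to the dozen expected deterioration events and compute a shifted odds ratio. Neither follows, because the deterioration outcome cannot miss a death under either threshold. The outcome that can miss one is the combined variable, for which the documents give no event rate. That variable is conditional on low frequency, although the summary of changes describes it as created for that reason.

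**Conclusion.** Two textual defects hold in the latest SAP.

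First, section 1 and 6.2 contradict 4.2 and the protocol on the deterioration threshold. Following 6.2 would remove every exactly-two-point worsening from an outcome with at most about 12 events in 400, leaving 9, 6 or 3 over the assumed range. This shows that worsening can be counted in two ways, not that it has been miscounted. The ceiling of 12 assumes that the rate seen at Amendment 3 holds to the end; some participants may not have completed 21 days when it was taken.

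Second, the protocol's death component is absent from SAP 4.2, the 6.2 event outcomes and the 6.2 combined variable, and no rule covers deaths in the secondary time-to-event analyses. The effect on the counts cannot be sized from the documents. That death counts as deterioration rests on a plain reading of the scale. The SAP does not say so, and carrying the primary outcome's censoring at death over to this outcome would undo it.

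These are secondary outcomes, so the primary conclusion is not touched. They are, however, the outcomes that speak to clinical benefit or harm beyond symptom duration.

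**What to change.** - In SAP sections 1, 4.2 and 6.2, use one definition: a rise of 2 or more points above the randomisation score, with death (category 7) counted as an event.
- Add death by day 21 to SAP 4.2, as the protocol lists it, and make it a component of the combined variable in 6.2.
- State in 6.2 how deaths are handled in the secondary Kaplan-Meier and Cox analyses of hospitalisation, oxygen and ICU, where death is a competing event.

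The cost is SAP wording only, best settled before unblinding. No new data are needed. The vital-status item is not scheduled on days 3 and 4, but the ordinal scale, which includes death, is recorded at randomisation and at every follow-up call (protocol 4.3.3).
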